6.4. Treatment Compliance**6.4.1. TRC105 Treatment Compliance**

All TRC105 infusions will occur at the trial site under the direct supervision of the treating physician or his or her designee.

6.4.2. Pazopanib Treatment Compliance

Patients will be asked to record the day and time of pazopanib home dosing on a TRACON supplied log to be reviewed by site personnel prior to initiation of each new cycle.

6.5. Patient Enrollment

Patients will be manually enrolled by TRACON Pharmaceuticals and assigned an eight digit patient number. This eight digit number will be used to identify patients throughout their participation in the trial. A regulatory binder will be provided and will include detailed instructions for the manual enrollment process.

5.3.5.2 Clinical Protocol

7. ASSESSMENT OF EFFICACY

7.1. Radiological Tumor Assessment

The primary efficacy endpoint for phase 2 is PFS, defined as time from screening to either first disease progression or death from any cause per RECIST version 1.1 [68]. Patients alive at the time of analysis will be censored at the date of last disease assessment.

The primary efficacy assessment will be best overall response as defined in Section 7.1.2. The determination of antitumor efficacy will be based on objective tumor assessments made by the Investigator according to RECIST version 1.1 [68]. Investigators will make treatment decisions based on these assessments. All lesions will be classified as target or non-target lesions at the Screening visit. Each lesion designation will be maintained through the course of the study.

The same method and technique should be used to characterize each identified and reported lesion at Screening, during the study treatment period, and at the End of Study visit. Imaging-based evaluation over clinical examination is the required technique when both could be used to assess the antitumor effect of the treatment. Clinical Oncology review of all tumor measurements is desired.

Whenever possible, clinical evaluation of superficial lesions should not be used as the sole form of measurement. However, when necessary, color photograph with metric caliper is acceptable. Tumor evaluation by positron emission tomography (PET) scan or by ultrasound may not substitute for CT or MRI scans.

Radiological tumor assessments will be performed at screening, as outlined in the Schedule of Assessments (Table 4, Table 5, Table 6 and Table 7), and whenever disease progression is suspected. Another tumor assessment will be performed at the End of Study Visit if an assessment has not been performed within the prior 8 weeks. All patient files and radiological images must be available for CRF source verification.

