2.1.1. Angiogenesis and Advanced Soft Tissue Sarcoma

Sarcomas are rare tumors that originate from mesenchymal tissues (e.g., bone, cartilage, fat and muscle). In the United States, the incidence of bone and soft tissue sarcomas is approximately 13,000 new cases per year, leading to more than 5,000 deaths annually [13]. According to the WHO classification of 2002, over 70 different types of sarcoma have been described [14]. Localized tumors are curable but patients with metastatic disease have a median survival of approximately 12 months. Standard systemic chemotherapy regimens are poorly tolerated and of limited usefulness with response rates in the range of 10-40% [15].

Recently, the VEGFR TKI pazopanib was approved in patients with advanced soft tissue sarcoma who have received prior chemotherapy. Pazopanib improved progression free survival in chemotherapy refractory patients compared to placebo (PFS of 4.6 months with pazopanib versus 1.6 months with placebo) and was generally well tolerated, with the most common

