5.3.5.2 Clinical Protocol

4. INVESTIGATIONAL PLAN

4.1. Overall Study Design and Plan

4.1.1. Overview

All patients must sign a consent form prior to undertaking any study-related procedures. Prospective patients will be screened to determine if they qualify for the study within 28 days of enrollment. Toxicities will be graded according to the NCI CTCAE Version 4.0.

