4.1.2.1. Screening

The following screening procedures must be performed within 28 days prior to the first day of study therapy. Qualifying hematology (including Fe studies), serum chemistry (including TSH testing), coagulation, physical examination, ECG, pregnancy and urinalysis collected within 7 days of cycle 1 day 1 do not need to be repeated. The following will be performed according to the Schedule of Assessments ([Table 4](#), [Table 5](#), [Table 6](#) and [Table 7](#)).

- Patient signature on current Institutional Review Board (IRB) approved informed consent form. Prior to undergoing any study-specific procedure, patients must read and sign the current Institutional Review Board (IRB) approved informed consent form. Patients may sign consent prior to the 28 day screening period.
- Medical history, baseline signs and symptoms, prior cancer therapy, prior cancer surgery, prior radiation therapy, drug allergies, primary diagnosis and demographics.
- Physical examination including examination of all major body systems, ECOG performance status, and vital signs.
- Hematology (including serum iron, ferritin and total iron binding capacity), coagulation (INR) and serum chemistry (including thyroid stimulating hormone (TSH)) to be performed locally.
- Serum or urine pregnancy test for all females of childbearing potential to be performed locally.
- Urinalysis to be performed locally. Microscopic analysis and/or urine protein-creatinine ratio (UPCR) should be performed as clinically indicated.
- CT or MRI scans of chest, abdomen and pelvis in addition to any other applicable sites of disease. Brain and bone scans to be performed if metastasis is suspected prior to starting the study. Color photography with caliper or ruler measurements should be used to assess cutaneous tumors (target lesions).
- Single tracing 12-Lead ECG (QT, PR and QRS intervals and heart rate will be captured).
- Assessment of concomitant medications and treatments from 28 days prior to the start of study treatment.

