13. **CT or MRI Tumor Imaging:** Images of the chest, abdomen, and pelvis to be performed at screening, and on-study as outlined in the assessment table. Known areas of disease should be consistently followed throughout the study. Assessments should be performed whenever disease progression is suspected. Allowable window for tumor imaging studies is +/- 7 days. Brain and bone scans are to be performed if metastases are suspected at screening or during study therapy. Color photography with caliper or ruler measurements, when possible, should be used to assess cutaneous tumors (target lesions).

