10.1.2. Phase 2 Statistical Design/Sample Size

Sixty three patients will be treated in the phase 2 portion of the study.

The study population for safety and efficacy will include all patients receiving at least a portion of one dose of TRC105.

Assuming a true median PFS of 4.6 months, a 9-month accrual period, a 6-month follow-up period, and based on the use of a one-sided test at the $\alpha=0.05$ level of significance, a sample size of 63 patients will provide 86% power to detect a 50% increase in the median PFS (i.e., a median of 6.9 months). These power estimates are based on the approach of Lawless [1].

Two additional phase 2 cohorts of up to 13 patients each with angiosarcoma will be enrolled into separate cohorts, angiosarcoma cohort 1 and 2. Angiosarcoma cohort 1: Assuming a 15% response rate by RECIST with pazopanib alone, 5 responders with TRC105 alone or in combination with pazopanib will provide >90% confidence the true response rate is >15% (two-sided exact 90% binomial with 5 of 13 responders is 16.57 and 64.52%). Angiosarcoma cohort 2: Assuming a 15% response rate by RECIST with pazopanib alone, 5 responders with TRC105 in combination with pazopanib will provide >90% confidence that the true response rate is >15%.

For each of the angiosarcoma cohorts, the two-sided exact 90% binomial with 5 of 13 responders is 16.57% and 64.52%.

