10.2.1.2. Phase 2 Analysis of Primary Objective

The primary analysis will test the null hypothesis that the median PFS is equal to 4.6 months. The time-to-event distribution for PFS will be estimated using the Kaplan-Meier method and the analysis will be based on the two-sided 90% confidence interval for the median (equivalent to the use of a one-sided test at the $\alpha=0.05$ level of significance).

Additional exploratory analyses of PFS will be conducted in subgroups defined based on number of prior therapies (one versus two or more), histology, and endoglin expression on sarcoma tissue.

For the angiosarcoma cohorts, the overall response rate and median duration of response by RECIST 1.1 will be calculated and the response rate will include the two-sided 90% confidence interval.

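### Phase 2 PFS is timed from screening, up to 28 days before first dose, in a single-arm test against a fixed 4.6 months; unless that benchmark has the same origin, the test leans toward success

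*Combined protocol and SAP*

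**What the plan says.** Section 7.1 is the only place that gives a starting point for PFS: "The primary efficacy endpoint for phase 2 is PFS, defined as time from screening to either first disease progression or death from any cause". The statistics sections (10.1.2 and 10.2.1.2) do not restate or change it.

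Section 4.1.2.1 sets how early screening may be: "The following screening procedures must be performed within 28 days prior to the first day of study therapy". Section 4.1.1 counts the same 28 days to a different point: "Prospective patients will be screened to determine if they qualify for the study within 28 days of enrollment". Consent is listed among the screening procedures, but "Patients may sign consent prior to the 28 day screening period". No single screening procedure is named as time zero.

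The analysis set is restricted to treated patients: "The study population for safety and efficacy will include all patients receiving at least a portion of one dose of TRC105" (Section 10.1.2). Section 10.1.2.1 narrows efficacy further, to patients with baseline and follow-up tumour measurements.

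The test is against a constant: "The primary analysis will test the null hypothesis that the median PFS is equal to 4.6 months" (Section 10.2.1.2), using the 90% confidence interval for the Kaplan-Meier median. Section 2.6.2 explains that the comparison is with pazopanib alone in an earlier study. Section 2.1.1 gives the figure, "PFS of 4.6 months with pazopanib versus 1.6 months with placebo", without saying from when it was counted.

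**The concern.** In a randomised trial, a time origin before treatment lengthens both arms alike. Here there is one arm and a fixed number. A patient must survive to dosing to enter the analysis, and Table 6 schedules no on-study scan before day 22 of cycle 2, so the interval from screening to first dose is almost event-free by construction. Under Section 7.1 that interval counts as progression-free time.

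If the 4.6 months was counted from randomisation or first dose, pre-treatment time is credited to the combination in the primary test, and its amount depends on clinic scheduling. The origin is also not one date: it could be read as the scan, another screening procedure, or consent. Two analysts could get different primary results from the same data.

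**Working it through.** **Inputs.** N = 63, null median 4.6 months, alternative 6.9 months, one-sided alpha 0.05, 9 months accrual, 6 months follow-up (Section 10.1.2). Longest gap 28 days (Section 4.1.2.1). Scans on day 22 of even cycles (Table 6), which is about days 50, 106 and 162; footnote 13 adds "Allowable window for tumor imaging studies is +/- 7 days". One month is 30.4375 days, so 4.6 months is day 140.

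**The plan's own figure.** With exponential PFS and uniform accrual, expected events are 63 × [1 − (e^(−6λ) − e^(−15λ))/(9λ)], where λ = ln 2/median. This gives 49.0 under the null and 40.3 under the alternative. Power = Φ[(ln 1.5 − 1.645/√49.0) × √40.3] = 86.1%. The stated 86% reproduces.

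**Gap against target effect.** The target gain is 6.9 − 4.6 = 2.3 months. A 14-day gap is 14/30.4375 = 0.46 months, and 0.46/2.3 = 20%. A 28-day gap is 0.92 months, and 0.92/2.3 = 40%.

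**Rejection rule.** With at least 6 months of follow-up, no one is administratively censored before 4.6 months. If x of 63 patients have a recorded event by then, S = 1 − x/63 and Greenwood's sum is V = x/[63(63 − x)]. The lower 90% limit for the median exceeds 4.6 months when the lower limit for S at that time is above 0.5.

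- Log-log interval: the limit for S is 0.510 at x = 24 and 0.494 at x = 25, so the test rejects at x ≤ 24.
- Linear interval: 0.502 at x = 25 and 0.485 at x = 26, so it rejects at x ≤ 25.

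**Null.** The benchmark is assumed to run from randomisation or first dose. The latent exponential median is set so that, at zero gap, half of patients have a recorded event by 4.6 months. Then P(X ≤ 24) = 3.8% and P(X ≤ 25) = 6.5% for X ~ Bin(63, 0.5).

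**Adding a gap of s days.** An event now counts by 4.6 months only if it is recorded by day 140 − s from first dose. The documents do not give the share q of events found off-schedule, so a range is shown. Scan 2 is taken as uniform over days 99-113.

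- q = 1 (continuous detection, latent median 4.6 months). At 14 days, p = 1 − 2^(−4.14/4.6) = 0.464. At 28 days, p = 1 − 2^(−3.68/4.6) = 0.426.
- q = 0 (scheduled scans only, latent median 3.48 months). At 14 days the cut-off is day 126, after the latest scan 2 (day 113), so p stays at 0.500. At 28 days it is day 112, so about 1 in 14 second scans falls too late and p = 0.483.
- q = 0.5 (latent median 4.01 months): p = 0.481 at 14 days and 0.453 at 28 days.

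One-sided error (log-log / linear):

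| Gap | q = 0 | q = 0.3 | q = 0.5 | q = 1 |
|---|---|---|---|---|
| 0 days | 3.8 / 6.5% | 3.8 / 6.5% | 3.8 / 6.5% | 3.8 / 6.5% |
| 14 days | 3.8 / 6.5% | 5.6 / 9.1% | 7.0 / 11.2% | 11.5 / 17.3% |
| 28 days | 6.7 / 10.7% | 11.3 / 17.0% | 15.3 / 22.1% | 27.9 / 37.1% |
| Uniform 0-28 days | 3.9 / 6.6% | 5.7 / 9.2% | 7.1 / 11.3% | 11.7 / 17.4% |

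A separate simulation of the Kaplan-Meier interval under continuous detection gave 12.2 / 17.4% at 14 days and 27.8 / 36.7% at 28 days, in agreement with the last column.

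**A different null.** If the true, not the recorded, progression median is 4.6 months, the simulated log-log error at gaps of 0, 14 and 28 days is 37.1, 37.4 and 46.7% (q = 0), 22.4, 28.5 and 40.6% (q = 0.3), and 15.4, 22.1 and 37.2% (q = 0.5). The high starting values come from detecting progression at intervals, which is a separate matter. The gap adds about 0 to 7 points at 14 days and 10 to 22 at 28 days.

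**The case against.** The strongest reply is that the bias depends on a fact outside the documents. If the 4.6 months was itself counted from screening with a similar gap, the effect largely cancels. That is correct. The concern is conditional on it, and the protocol gives no means of checking.

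Second, the effect may be nil. With scheduled detection only, a 14-day gap does nothing. The 28-37% figure needs every patient at the 28-day maximum and continuous detection, which scans about eight weeks apart do not provide. This also stands: the rates are scenarios, not estimates. However, scans are also required whenever progression is suspected and deaths are not tied to visits, so purely scheduled detection is a limiting case too. In no modelled scenario does the gap lower the error.

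Third, the rejection rule ignores dropout, although patients can leave early and Section 10.1.2.1 may take the denominator below 63. That is a fair criticism of the arithmetic. Adding 10-30% dropout by 4.6 months, under continuous detection with the log-log limit, leaves about 12% at 14 days and 26-28% at 28 days, so it does not change the picture. The smaller denominator was not modelled.

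Fourth, tumour sums are fixed at screening (Section 7.1.1.1), so growth before dosing can bring progression forward at the first on-study scan. This is a genuine partial offset. It is not modelled, and it does not remove the added time.

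Fifth, early consent lies outside the 28-day period and so need not blur the screening date. That weakens the consent point but still leaves several procedures and no named one.

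**Conclusion.** The concern holds as stated. The only PFS origin in the plan credits treated patients with 0 to 0.92 months of nearly event-free time before treatment, in a single-arm test against a constant of unstated origin. If the benchmark runs from randomisation or first dose, the one-sided error moves from 3.8-6.5% at zero gap to 3.8-17% at 14 days and 7-37% at 28 days. The effect is small if nearly all events are found on scheduled scans and material if many are not. These ranges assume exponential PFS, the scan timing above and no pre-dose growth; neither the actual gaps nor the off-schedule share is in the documents. If the benchmark shares the screening origin, the bias largely disappears. This should be fixed. Confidence is medium, because the size rests on those unknowns and on the benchmark's origin.

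**What to change.** In Section 7.1, define phase 2 PFS as time from first dose of study treatment (cycle 1 day 1) to first RECIST 1.1 progression or death, and keep the screening scan only as the baseline for tumour measurement. In Section 10.2.1.2, state the time origin of the 4.6-month benchmark and confirm that it matches. If the benchmark proves to have another origin, such as randomisation, say so and add a sensitivity analysis on the closest matching origin.

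The same paragraph of Section 7.1 censors patients who are alive. It should say alive and progression-free, censored at the last disease assessment. This is a wording correction, and the conclusion here does not rest on it.

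The cost is two sentences in Section 7.1 and one clause in Section 10.2.1.2. The dates are already collected, and visits, treatment and sample size are unchanged. The drawback is that reported PFS becomes shorter by the screening-to-dose gap, 0 to 0.92 months.

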7.1.1. Measurability of Tumor Lesions

At Screening, individual tumor lesions will be categorized by the Investigator as either target or non-target according to RECIST 1.1 as described below.

- **Measurable:** Lesions that can be accurately measured in at least one dimension (longest diameter to be recorded) as ≥ 10 mm with spiral CT scan. Lytic bone lesions, with an identifiable soft tissue component, evaluated by CT or MRI, can be considered measurable lesions if the soft tissue component otherwise meets the definition of measurability previously described. Blastic bone lesions are non-measurable. Lesions in previously irradiated areas (or areas treated with local therapy) should not be selected as target lesions, unless there has been demonstrated progression in the lesion. Clinical lesions will only be considered measurable when they are superficial (e.g. skin nodules, palpable lymph nodes) and ≥ 10 mm. Clinical lesions must be measured with calipers.
- **Non-Measurable:** All other lesions, including small lesions and bone lesions other than lytic bone lesions, leptomeningeal disease, ascites, pleural or pericardial effusions, lymphangitis of the skin or lung, abdominal masses that are not confirmed and followed by imaging techniques, previously irradiated lesions (unless there has been demonstrated

5.3.5.2 Clinical Protocol

progression in the lesion), and disease documented by indirect evidence only (e.g. by laboratory tests such as alkaline phosphatase).

7.1.1.1. Recording Tumor Measurements

Measurable lesions up to a maximum of 5 lesions representative of all involved organs (with a maximum of 2 lesions per organ) should be identified as target lesions and measured and recorded at Screening and at the stipulated intervals during treatment. Target lesions should be selected on the basis of their size (lesion with the longest diameters) and their suitability for accurate repetitive measurements (either by imaging techniques or clinically). Target lesions may include lymph nodes with a short axis ≥ 15 mm.

The longest diameter will be recorded for each target lesion (with the exception of lymph nodes, where the short axis will be used). The sum of the diameter for all target lesions at Screening will be calculated and recorded as the baseline sum diameter to be used as reference to further characterize the objective tumor response of the measurable dimension of the disease during treatment. All measurements should be performed using a caliper or ruler and should be recorded in metric notation in millimeters.

All other lesions (or sites of disease) should be identified as non-target lesions and should also be recorded at baseline. Measurements are not required and these lesions should be followed as “present”, “stable”, “absent”, “increased” or “decreased”.

7.1.2. Definitions of Tumor Response

7.1.2.1. Target Lesions

- **Complete response (CR)** is defined as the disappearance of all target lesions.
- **Partial response (PR)** is defined as a $\geq 30\%$ decrease in the sum of the dimensions of the target lesions taking as a reference the baseline sum dimensions.
- **Progressive disease (PD)** is defined as a $\geq 20\%$ relative increase and ≥ 5 mm absolute increase in the sum of the dimensions of the target lesions taking as a reference the smallest sum of the dimensions recorded since the treatment started, or the appearance of one or more new lesions.
- **Stable disease (SD)** is defined as neither sufficient shrinkage to qualify for PR nor sufficient increase to qualify for PD taking as a reference the smallest sum of the dimensions since the treatment started.

7.1.2.2. Non-Target Lesions

- **Complete response (CR)** is defined as the disappearance of all non-target lesions.
- **non-CR/non-PD** is defined as a persistence of ≥ 1 non-target lesions.
- **Progressive disease (PD)** is defined as unequivocal progression of existing non-target lesions, or the appearance of ≥ 1 new lesions.

5.3.5.2 Clinical Protocol

The cytological confirmation of the neoplastic origin of any effusion that appears or worsens during treatment when the measurable tumor has met criteria for response or stable disease is mandatory to differentiate between response or stable disease and progressive disease.

7.1.2.3. Determination of Overall Response**7.1.2.3.1. By RECIST**

When both target and non-target lesions are present, individual assessments will be recorded separately. The overall assessment of response will involve all parameters as depicted in [Table 15](#). Per RECIST 1.1, in non-randomized trials with response as a primary endpoint, confirmation of PR or CR is required. Per RECIST 1.1, a modest increase in the size of one or more non-target lesions is usually not sufficient to qualify for unequivocal progression status.

Table 15: Response Evaluation Criteria in Solid Tumors

Target Lesions ^a	Non-target Lesions ^b	New Lesions ^c	Overall Response
CR	CR	No	CR
CR	Non-CR/non-PD	No	PR
CR	Not evaluated	No	PR
PR	Non-PD or not all evaluated	No	PR
SD	Non-PD or not all evaluated	No	SD
Not all evaluated	Non-PD	No	Not Evaluable
PD	Any Response	Yes or No	PD
Any Response	PD	Yes or No	PD
Any Response	Any Response	Yes	PD

^aMeasurable lesions only.

^bMay include measurable lesions not followed as target lesions or non-measurable lesions.

^cMeasurable or nonmeasurable lesions.

The best overall response is the best response recorded from the start of the treatment until disease progression/recurrence (taking as reference for progressive disease the smallest measurements recorded since the treatment started). The patient's best response assignment will depend on the achievement of both measurement and confirmation criteria.

NOTE: Patients with a global deterioration of health status requiring discontinuation of treatment without objective evidence of disease progression at that time should be reported as "Need for additional anti-cancer therapy/surgery". Every effort should be made to document the objective progression even after discontinuation of treatment.

In some circumstances, it may be difficult to distinguish residual disease from normal tissue. When the evaluation of complete response depends upon this determination, it is recommended that the residual lesion be investigated by fine needle aspirate or biopsy before confirming the complete response status.

